## 1. BACKGROUND

Premature ventricular complexes (PVCs) are a frequent target for catheter ablation. Conventional mapping of ventricular tachycardia (VT) requires that the operator accurately detects the local activation time (LAT) in unipolar (U-EGM) and/or bipolar electrograms (B-EGM). The maximal  $-dV/dt$  in the U-EGM coincides with the arrival of the depolarization wavefront directly beneath the electrode. Furthermore, the morphology of the unipolar recording indicates the direction of wavefront propagation. However, the major disadvantages of U-EGMs are susceptibility to noise and the presence of substantial far-field signal,, which limit their routine use during activation mapping. In B-EGMs, the far-field signal is subtracted out, facilitating the identification of local activation signal, which coincides with the initial peak of the B-EGM. Drawbacks to B-EGMs include being influenced by wavefront direction, bipole orientation, electrode size, and interelectrode spacing. Furthermore, LAT assessment on B-EGMs is often challenging, especially in cases with low-voltage EGMs with multiple components.

Given these limitations of conventional assessment of LAT in both bipolar and unipolar EGMs, increasing efforts have attempted to develop automatic algorithms for activation mapping. Recently, El Haddad et al described an automated algorithm that detects the maximal  $-dV/dt$  in the U-EGM within the window demarcated by the B-EGM that achieved the highest accuracy in algorithmic mapping of atrial and ventricular tachycardia. This algorithm, once integrated into an electroanatomical navigation system, allows the automatic annotation of the LAT during activation mapping. However, data about its utility and accuracy in PVC ablation procedures are scarce. A recent study by our group including 40 patients that underwent PVC ablation showed that the correlation between manual LAT annotation by expert electrophysiologists and automatic annotation by the Wavefront system was good. However, WF-annotation systematically underestimated LAT, especially in LVOT. In terms of accuracy in the SOO identification, the effective RFp was equally well identified with both annotation approaches. However, a randomized study comparing ablation guided by conventional LAT annotation vs. guided by automatic LAT annotation should be performed in order to confirm the efficacy of Wavefront-guided annotation during PVC ablation procedures.

The present randomized study aims to analyze the accuracy of this novel algorithmic method, based on automatic annotation of the maximal negative slope of the U-EGM within the window demarcated by the B-EGM (Wavefront, CARTO, Biosense Webster, Diamond Bar, CA, USA) by comparison with conventional manual annotation in a multicenter cohort of patients referred for PVC ablation. Further on, the automatic annotation of LAT will be aided by the ECG recognition pattern algorithm (included in the last version of CARTO), which is intended to avoid wrong annotation of ventricular complexes other than the clinical PVC. This automatic acquisition process

(LAT and ECG pattern) will be referred to from now on as WF-method. We hypothesize that automatic LAT annotation using WF-method could be superior to conventional, manual annotation in terms of mapping success and could reduce both procedure time and radiofrequency time.

## 2. STUDY PURPOSE

### 2.1 STUDY DESIGN

This is a prospective, randomized, controlled and international multicenter study.

### 2.2 RANDOMIZATION

All patients who fulfill the inclusion criteria will be consecutively enrolled and randomized on a 1:1 basis to each of the LAT annotation systems (WF vs. M-method) before the ablation procedure. Ablation will be directed to the earliest activation site identified with the assigned annotation system. Any change of the assigned annotation system during the procedure will not be allowed, thus being a reason for justifying study exclusion. **The only exception will be considered when using the WF-method, if annotation is misleading due to the presence of atrial far-field signals in the selected window of interest (see section 4.5.3). In those cases, whether elimination of the acquired point or manual reannotation will be admitted, after description of the issue.**

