### 2.4 DEFINITIONS

- **Mapping success:** It will be defined as complete PVC abolition after RF applications at the earliest activation site (EAS) identified using the assigned mapping approach. A maximum of 2 RF applications with appropriate parameters (contact force, impedance drop, catheter stability) during a maximum of 45 seconds will be allowed. If the PVC is not abolished after 2 RF applications with appropriate parameters, mapping will not be considered successful.
- **Acute procedure success:** It will be defined as complete elimination of the PVC at the end of the procedure.

- **Target point:** It will be defined as any suspected PVC-SOO where RF is delivered according to mapping data. Therefore, for one case there can be found a single target point with multiple RF applications, or multiple target points with one single RF application. The maximum distance between 2 RF applications to be considered at the same target point will be defined as 5 mm (equivalent to a 1-cm^2 area).
- **First mapped chamber:** It will be defined as the first cardiac chamber where the operator decides to perform electroanatomical mapping according to electrocardiographic (PVC morphology) and clinical criteria. In the case of PVCs arising from ventricular outflow tracts, we propose an algorithm (see Appendix C) to avoid subjective criteria, and to deal with eventual wrong selection of the first mapped chamber, leading to unnecessary RF applications.

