#### 2.6.2 EXCLUSION CRITERIA

Patients will be excluded from the study if they meet any of the following criteria:

- Age < 18 years.
- Pregnancy.
- PVC ablation procedures guided by pacemapping (PASO® module); eg. low burden of PVCs during the study, mechanical impact during activation mapping.
- Impossibility to perform activation mapping with the required density of points in the region of interest (see section 4.5.3).
- Concomitant investigation treatments.
- Medical, geographical and social factors that make study participation impractical, and inability to give written informed consent. Patient's refusal to participate in the study.

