#### 4.5 RANDOMIZATION AND ABLATION

##### 4.5.1 RANDOMIZATION

Patients will be randomly assigned to each of the annotation systems (WF vs. M-method) on a 1:1 basis before the procedure as described in chapter 2.2.

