##### 4.5.3 ACTIVATION MAPPING. ANNOTATION SYSTEMS.

The cardiac structures that will be targeted during activation mapping will be decided according to PVC morphology in surface ECG and operator's criteria. A detailed activation map of the cardiac chamber/s suspected to contain the SOO of the will be performed in all patients:

- In those cases with a suspected outflow tract origin, mapping will be guided by a proposed algorithm (see Appendix C) that includes a previously described clinical score (1 point for

each of the following: hypertension, male gender, age > 50 years). With this algorithm, an accurate prediction of left vs. right ventricular outflow tract origin is expected.

- After applying the previous algorithm and having completed RVOT mapping, if a focus outside the RVOT is suspected, subsequent mapping of the coronary sinus may be advisable to add useful information of the left side and possible epicardial origin of the PVCs.
- The minimum density of points required to obtain an acceptable map will be defined as a fill threshold of < 6 mm in the 20-ms isochronal area containing the earliest activation site (area of interest), and < 10 mm for the chamber of interest.

An ECG surface lead with a well-defined R-wave peak (R peak = 0 ms) will be used as the reference to perform the activation EAM. For both annotation systems, the end of the window of interest will be set at the end of the PVC-QRS to avoid the annotation of atrial far-field signals (in cases with retrograde conduction of the PVC). During activation mapping, points will be acquired only after a 2-second period of catheter stability. Activation mapping of additional anatomical structures will be allowed under operator criteria, in cases where the suspected SOO could not be located at the initially mapped chamber. Regardless of the number of structures mapped during the procedure, the annotation system will be the one assigned at the beginning of the procedure. The earliest activation site (EAS) will be considered to be located at the point with the highest precocity relative to the earliest onset of PVC on the 12-lead surface ECG, when activation mapping has concluded.

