**ABLATION DATA:**

- **Number of ablation targets (describe locations briefly):**
  1. ....
  2. ....
  3. ....
- **Number of RF applications:** .....
- **Total RF time:** ..... sec
- **Site of origin (SOO, specify location):** .....
- **Number of points in SOO's chamber:** .....
- **Total number of points (all chambers):** .....
- **MAPPING SUCCESS?\***: NO / YES
- **ACUTE PROCEDURE SUCCESS\*\*:** NO / YES

\*Complete PVC abolition after NO MORE THAN 2 RF applications (< 45 seconds each) at the EAS identified using the assigned mapping approach (M vs. WF).

\*\*Complete elimination of the PVC at the end of the procedure.

- **Total procedure time:** Start: .....:..... Finish: .....:..... Total: ..... min

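### Section 2.2 makes a post-randomisation change of annotation system a reason for exclusion; before success, the same patient is a failure under 2.4, and 5.2 names no analysis set

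*Combined protocol and SAP*

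**What the plan says.** **Timing.** Sections 2.2 and 4.5.1 place allocation ahead of mapping: patients are assigned "on a 1:1 basis before the procedure as described in chapter 2.2". Section 4.5.3 holds the operator to that assignment however many structures are mapped: "the annotation system will be the one assigned at the beginning of the procedure".

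**Exclusion after allocation.** Section 2.2 states: "Any change of the assigned annotation system during the procedure will not be allowed, thus being a reason for justifying study exclusion". It sets no time limit within the procedure. It makes one exception, in the WF arm only: a point distorted by atrial far-field signal may be deleted or reannotated by hand. Section 2.6.2 also excludes "PVC ablation procedures guided by pacemapping (PASO® module); eg. low burden of PVCs during the study, mechanical impact during activation mapping" and "Impossibility to perform activation mapping with the required density of points in the region of interest". Table 1 re-checks eligibility at baseline and not later.

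**Endpoint.** Section 2.4 defines mapping success as "complete PVC abolition after RF applications at the earliest activation site (EAS) identified using the assigned mapping approach", and adds: "If the PVC is not abolished after 2 RF applications with appropriate parameters, mapping will not be considered successful". The data sheet in Appendix B ties success to the assigned approach in the same way.

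**Analysis.** Section 5.2 gives the software, the summary statistics, the tests and the significance level. It does not say which patients enter the primary comparison, nor does any other section available to us. Section 2.7 provides an enrolment log that includes dropouts, and Table 1 has rows for protocol deviation and termination. These record patients but do not say who is analysed.

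**The concern.** A change of annotation system happens after allocation and is made by an operator who knows the arm. It may itself be a sign that the assigned method was not working. If such patients leave the comparison, a method can lose some of its own failures, and the groups compared are no longer those that were randomised.

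The plan also gives one patient two possible fates, failure under 2.4 or exclusion under 2.2. With no analysis set named, either could be defended from the text after the results are known. The comparison affected is the primary endpoint of a randomised superiority trial.

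**Working it through.** **1. Fate of a switched patient.** Section 2.4 does not mention switches, so the middle column is inferred from its wording.

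| When the system is changed | Under 2.4 | Under 2.2 |
|---|---|---|
| Before any RF application | No success: the site was not found with the assigned system | Excludable |
| After two failed applications | No success, by the two-application rule | Excludable |
| After abolition at the assigned-method site | Success | Excludable |

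The sections conflict in every row. In the first two, exclusion removes a failure.

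**2. The plan's own sample size.** Inputs from 5.1: 60% (M) vs 85% (WF), two-sided 5%, power 80%. With pooled variance under the null and mean rate 0.725:

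n = [1.960 × √(2 × 0.725 × 0.275) + 0.842 × √(0.60 × 0.40 + 0.85 × 0.15)]² / 0.25² = 48.9, so 49 per group and 98 in total.

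The stated figure reproduces. Section 2.7 plans 100, taken here as 50 per arm.

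**3. Type I error if patients are excluded.** The documents give no exclusion rates, so all rates here are assumptions. In each arm a share e is excluded, of whom a share s would have been failures. The number retained is Bin(50, 1−e), with success rate (p − e(1−s))/(1−e). The test is the uncorrected chi-square, evaluated by exact enumeration. For p = 0.60 and e = 10%, the retained rate is 0.60/0.90 = 66.7% if all are failures and 0.55/0.90 = 61.1% if half are.

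True success 60% in both arms:

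| Excluded, one arm and the other | All failures | Three quarters | Half |
|---|---|---|---|
| None | 5.2% | 5.2% | 5.2% |
| 5% and 10% | 6.5% | 5.5% | 5.1% |
| 0 and 10% | 10.4% | 6.8% | 5.2% |

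With 5% excluded from each arm, all failures, the error is 5.1%: equal loss does not inflate it. Excluding 10% of an arm as failures removes 0.10/0.40 = one quarter of that arm's failures.

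At 85% success the base figure is 5.5%. Excluding 5% of one arm gives 9.9% if all are failures and 5.8% if half are. The first removes 0.05/0.15 = one third of that arm's failures.

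**4. Fixed counts, M vs WF.**
- Near the planned effect, 30/50 vs 42/50 gives p = 0.008. Dropping five M failures (30/45) gives 0.049, and dropping six (30/44) gives 0.071.
- At a smaller effect, 30/50 vs 37/50 gives p = 0.137. Dropping two WF failures (37/48) gives 0.069, and dropping three of the 13 (37/47) gives 0.046.

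**The case against.** **The rule may not mean removal from the analysis.** Exclusion from the study could mean withdrawal from follow-up only. A reader might infer that the plan states these patients are dropped from the primary comparison. It does not, and the flow chart is not shown to us. This stands. It leaves the analysis set open, which is the defect.

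**Not every switched patient is a failure.** A reader might infer that 2.4 scores all of them as no success. It does not: a patient whose ectopy was abolished at the assigned-method site before the switch has met the definition. This stands.

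**No bias is demonstrated.** Uneven loss is plausible for switches, but nothing in the documents shows it. Nothing suggests an arm difference for point density, low burden or mechanical impact. If half of those excluded would have failed, inflation is negligible at 60% success. The largest figures assume that all were failures in one arm, which is exact only for switches after two failed applications. This stands as a limit on size.

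**Some exclusions can be applied in time.** The baseline re-check in Table 1 can catch those evident by then, possibly including low burden. It cannot catch events during mapping.

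**Power.** Because 100 are enrolled against 98 required, a reader might infer room for only two exclusions. That is too strong: with 5% of each arm left out at random, power is still about 80%, and at 10% about 78%. The documents do not say whether excluded patients are replaced.

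**Conclusion.** The point holds. Section 2.2 attaches exclusion to an event that follows randomisation, section 2.4 would score most such patients as failures, and section 5.2 does not say which prevails. Following 2.2 can therefore remove failures of the assigned method from its own arm.

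The size cannot be determined from the documents. At 60% success, the assumed rates examined give a type I error between about 5% and 10.4%. It depends on how uneven the loss is and how many of those lost would have failed. At the planned effect the conclusion is robust, since six M failures would have to be dropped to lose significance. At smaller effects a few exclusions in one arm can decide the result. The case for change rests on the contradiction and the missing analysis set, not on a demonstrated bias.

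**What to change.** **Section 2.2.** Replace exclusion with recording the change as a protocol deviation.

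**Section 5.2.** Add:

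> The primary analysis includes all randomised patients in their assigned group. A change of annotation system before mapping success is reached counts as no mapping success. In the WF arm, deleting a point or reannotating it by hand because of atrial far-field signal, as section 2.2 permits, is not a change of system.

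The last sentence is needed. Without it, permitted corrections could be scored as failures in one arm only.

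**Section 2.6.2.** Apply the pacemapping and point-density items as exclusions only where they are known before allocation. If either arises later, keep the patient in the assigned arm and pre-specify one scoring rule, identical in both arms, with the alternative handling as a sensitivity analysis. This adds to 2.4, which has no density condition.

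**Reporting.** Keep the present exclusions as a per-protocol sensitivity analysis and report these events by arm and reason. The data sheet has a single field for the annotation system; record the assigned and the used system separately.

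**Cost.** The edits are wording and a few data fields, but scoring events as failures costs power. Assume 60% vs 85% among the other patients and 50 per arm:

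- With 5% of each arm scored as failures, the rates become 0.95 × 60% = 57.0% and 0.95 × 85% = 80.8%. Power falls from 82% to 74%.
- With 10% scored, they become 54.0% and 76.5%, and power is 66%.
- If such events occur only in WF, power is 63% at 5% and 43% at 10%. If only in M, it is 89% and 94%.

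Restoring 80% power by the formula used above would take 59 per arm (118) at 5% of each arm, or 70 per arm (140) at 10%. The protocol should restate its power for the rate it expects, or raise the sample size.

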### 2.3 OBJECTIVES

In order to assess the potential benefits of automatic instead of manual LAT annotation during ablation procedures of premature ventricular complexes (PVCs), the following objectives will be assessed:

1. To compare the ability of both annotation systems (WF vs. M-method) to accurately identify the PVC site of origin (SOO) and propagation pattern. To compare the rates of mapping success (see definition in the next section) between both methods.
2. To assess other procedural outcomes obtained from both annotation systems: Procedure time, mapping time, RF time, number of RF applications.
3. To compare the clinical outcomes (PVC burden at one month after procedure) between both annotation approaches.

### 2.4 DEFINITIONS

- **Mapping success:** It will be defined as complete PVC abolition after RF applications at the earliest activation site (EAS) identified using the assigned mapping approach. A maximum of 2 RF applications with appropriate parameters (contact force, impedance drop, catheter stability) during a maximum of 45 seconds will be allowed. If the PVC is not abolished after 2 RF applications with appropriate parameters, mapping will not be considered successful.
- **Acute procedure success:** It will be defined as complete elimination of the PVC at the end of the procedure.

- **Target point:** It will be defined as any suspected PVC-SOO where RF is delivered according to mapping data. Therefore, for one case there can be found a single target point with multiple RF applications, or multiple target points with one single RF application. The maximum distance between 2 RF applications to be considered at the same target point will be defined as 5 mm (equivalent to a 1-cm^2 area).
- **First mapped chamber:** It will be defined as the first cardiac chamber where the operator decides to perform electroanatomical mapping according to electrocardiographic (PVC morphology) and clinical criteria. In the case of PVCs arising from ventricular outflow tracts, we propose an algorithm (see Appendix C) to avoid subjective criteria, and to deal with eventual wrong selection of the first mapped chamber, leading to unnecessary RF applications.

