## 2.5 ENDPOINTS

### 2.5.1 PRIMARY ENDPOINT

The primary endpoint will be mapping success using the assigned mapping approach, as defined in the previous section.

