##### 4.5.2 ELECTROPHYSIOLOGIC STUDY

Electroanatomical mapping (EAM) will be performed using the CARTO® navigation system (Biosense Webster, Diamond Bar, CA) with a 3.5-mm irrigated tip catheter (NaviStar® ThermoCool® or ThermoCool® SmartTouch®, Biosense Webster). During the procedure, 12-surface ECG and intracardiac recordings will be displayed by an electrophysiology data acquisition system (Bard LabSystem, CR Bard Inc, Lowell, MA; or EP-Tracer, CardioTek, Maastricht, The Netherlands).

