**ABLATION PROCEDURE:**

- **Annotation system:** MANUAL / WAVEFRONT
- **Ablation catheter:** Navistar ThermoCool / ThermoCool SmartTouch
- **Deflectable sheath (Agilis):** NO / YES
- **First vascular access:** Femoral artery / femoral vein

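### Mapping failure is scored only after two RF applications with appropriate parameters, but the data sheet records none of those parameters and its scoring footnote drops the condition

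*Combined protocol and SAP*

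**What the plan says.** Section 2.5.1 makes mapping success the primary endpoint: "The primary endpoint will be mapping success using the assigned mapping approach, as defined in the previous section". The definition in section 2.4 has two parts that matter here.

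- Which applications are permitted: "A maximum of 2 RF applications with appropriate parameters (contact force, impedance drop, catheter stability) during a maximum of 45 seconds will be allowed".
- When the patient is a failure: "If the PVC is not abolished after 2 RF applications with appropriate parameters, mapping will not be considered successful".

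No threshold is given for contact force, impedance drop or stability, and nobody is named to judge them.

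Appendix B collects the data that would support the score. Under Ablation Procedure it records the catheter type, "Navistar ThermoCool / ThermoCool SmartTouch". Under Ablation Data it asks for the ablation targets, "Number of RF applications" as one total, total RF time, and a yes/no for mapping success. The footnote to that yes/no begins "Complete PVC abolition after NO MORE THAN 2 RF applications (< 45 seconds each) at the EAS identified using the assigned mapping approach (M vs.". It does not mention appropriate parameters.

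Section 4.5.2 permits mapping "with a 3.5-mm irrigated tip catheter (NaviStar® ThermoCool® or ThermoCool® SmartTouch®, Biosense Webster".

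**The concern.** Whether an application was appropriate decides whether it counts towards failure, so that judgement is part of the primary endpoint. The plan neither defines it nor collects the data needed to make it or check it.

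In use, the condition tends to work in one direction. An application that abolishes the PVC gives nobody a reason to look back at its parameters. One that fails can be called inadequate and repeated. The person making that call knows the arm, because an electrophysiologist annotates each point under the manual method (4.5.3.1) and the mapping system does so under the automatic method (4.5.3.2). If the call is made more generously in one arm, the mapping success rates diverge for reasons unrelated to annotation accuracy.

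The footnote adds a second problem. A patient whose first application was judged inadequate, whose second failed and whose third succeeded is a success under 2.4 and a failure under Appendix B.

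**Working it through.** **Step 1: the two rules side by side**

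| | Section 2.4 | Appendix B |
|---|---|---|
| Applications that count | Two with appropriate parameters | Any two |
| Parameter criteria | Three named, no thresholds | Not mentioned |
| Parameter values recorded | – | None |
| Record per application | – | None; total count and total time only |
| Applications set aside, with reason | – | No field |

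The rule in 2.4 cannot be applied or audited from Appendix B. The rule in the footnote is a different rule.

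**Step 2: the plan's own sample size**

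Inputs from section 5.1 are 60% against 85%, type I error 5% and power 80%. I take the test as two-sided because the alternative is that the methods are not equal. With mean rate 0.725:

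n = [1.960·√(2·0.725·0.275) + 0.842·√(0.60·0.40 + 0.85·0.15)]² / 0.25² = 48.9, so 49 per group and 98 in total.

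This matches the plan and is not in dispute. I use 49 per arm below.

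**Step 3: a model for discounting**

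The documents give no rate of discounted applications, so these are assumptions:

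- True success within two applications is 60% in both arms.
- Attempts are independent with success probability q. Then 1 − (1 − q)² = 0.60, so q = 1 − √0.40 = 0.3675.
- A share s of patients who failed twice has one failure set aside and gets one more attempt.

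Observed success is p(s) = 0.60 + 0.40·s·0.3675. At 49 patients, 49 × 0.40 = 19.6 are expected to fail twice.

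**Step 4: false-positive rate, one arm discounted**

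This is the exact probability that the uncorrected two-sided chi-square test gives p < 0.05, summed over all pairs of binomial outcomes at 49 per arm, with 60% in the other arm.

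| s | p(s) | Patients given an extra attempt (19.6·s) | Expected to turn into successes | False-positive rate |
|---|---|---|---|---|
| 0 | 60.0% | 0 | 0 | 5.0% |
| 0.2 | 62.9% | 3.9 | 1.4 | 5.9% |
| 0.5 | 67.4% | 9.8 | 3.6 | 11.4% |
| 1 | 74.7% | 19.6 | 7.2 | 33.6% |

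**Step 5: other patterns under the same model**

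- *Same s in both arms, no true difference:* the false-positive rate stays at 4.8% to 5.0%.
- *s = 0.5 in one arm and 0.3 in the other:* 5.8%.
- *True rates 60% and 85%, manual arm only discounted:* exact power falls from about 81% to 72%, 54% and 25% for s = 0.2, 0.5 and 1.
- *True rates 60% and 85%, same s in both arms:* the automatic arm has q = 1 − √0.15 = 0.6127 per attempt. Power is 79.9%, 79.1% and 81.0%.

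The last result depends on the model. If equal discounting instead turns the same fraction of failures into successes in both arms (10%, 20% or 30%), power by the normal approximation falls from 80.1% to 74.0%, 67.1% and 59.6%.

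**The case against.** **A stronger reading a reader might infer.** Since 4.5.2 permits two catheters, one might conclude that contact force cannot be measured with one of them, so the failure rule could never be met for those patients. The documents do not support this. Section 4.5.2 and Appendix B name the catheters and say nothing about which of them measures force. The parenthesis in 2.4 can also be read as examples of adequate delivery rather than a strict three-part test. Catheter type is not tied to arm and allocation is randomised 1:1, so catheter choice alone need not bias the comparison. What remains is a question for the sponsor.

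**The rule is not one-sided as written.** Section 2.4 applies the condition to all permitted applications. That is correct; the asymmetry lies in how an unrecorded judgement is likely to be used.

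**The form prevents discounting.** On the footnote's rule no application can be set aside. This is true of the footnote, but 2.4 is the definition that section 2.5.1 invokes, and the two disagree.

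**The score can be checked in part.** A yes for mapping success with one target and more than two applications could be queried. That stands as a partial check. The count covers the whole procedure, however, and shows neither which applications were at the earliest site nor which were judged inadequate and why.

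**A third attempt is limited.** Section 4.5.4 moves the operator to another target point if PVCs persist after 30 seconds. This reduces the scope for repeats, though the same section also provides for further applications within the same target point.

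**The figures are a worst case.** Repeats at the same wrong site probably fail together, so 36.8% for a third attempt is likely too high, and s = 1 is extreme. Both points stand.

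**Conclusion.** The concern holds as a gap in how the primary endpoint is scored. The data needed to apply the stated failure rule are not collected, the scoring form uses a different rule, and the judgement rests with someone who knows the arm, with no blinded adjudication described in the available text.

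Nothing in the documents shows that unequal discounting occurs; it is a risk. Its effect is small if a fifth of double failures in one arm get an extra attempt (5.9% against 5.0%) and material from about half (11.4%), with 33.6% as the extreme. These figures rest on one-arm discounting, independent attempts and 60% true success in both arms. Equal discounting leaves the false-positive rate near 5%. The sample size of 98 is unaffected.

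**What to change.** 1. Reconcile section 2.4 with the Appendix B footnote so that one counting rule scores the primary endpoint. Counting every application, as the footnote does, would remove the problem, but it should be a deliberate choice.
2. If the condition on parameters is kept, have the investigators fix the criteria before the first patient. Add a line per application to Appendix B: parameter values, whether it qualifies and the reason if not, and whether the PVC was abolished.
3. Score successful and failed applications in both arms from those recorded values, preferably by assessors blind to arm.
4. Add a sensitivity analysis of mapping success that counts every application.
5. Ask the sponsor to confirm that each listed parameter can be recorded with both permitted catheters and, if not, how the condition is applied. The choice of catheter and of parameter limits stays with the investigators.

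The cost is a wording change in 2.4, a few more lines on the data sheet and one extra analysis. Assessors blind to arm, if used, add some work.
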